The timing of activities is shown in the table below. We will strive to schedule patients within two weeks of enrollment, although some visits will fall outside of that window due to conflicts in the patients' schedules and no-showed or rescheduled appointments. Patients will attend a 3-hour pre-treatment visit at the Indiana CTSI Clinical Research Center. To minimize the effect of extraneous factors on FMD,^{169,170} patients will be told to fast and to avoid tobacco and exercise for ≥ 8 hours before their visit. The exam room will be kept at 68-71°F, and premenopausal women will be scheduled within 2 weeks of menstruation onset. Patients will have their height, weight, and BP measured; will complete self-report scales on a secure SurveyMonkey website designed for this study visit; and will undergo FMD and heart rate variability assessments and a blood draw (standard venipuncture). To end this visit, the randomization procedure will be initiated, the patient and the treatment team will be notified of the assignment, and the mid-treatment call and post-treatment visit will be scheduled. If the patient is randomized to the eIMPACT intervention, the depression clinical specialist will conduct a brief session over FaceTime to orient the patient to intervention materials and to schedule the initial assessment. The FaceTime session will not be recorded. Within 2 weeks, the depression clinical specialist will call eIMPACT patients to initiate treatment, and a research assistant will send a letter to the primary care providers of usual care patients to notify them that their patient has a depressive disorder and to encourage follow-up. Approximately six months after randomization, research assistants will contact all patients to complete the 45-min mid-treatment call. First, a brief questionnaire used in our pilot trials will be administered to assess for the occurrence of CVD events since enrollment. As we have also done in our pilot projects, the self-reported scales completed at pre-treatment will then be readministered. Approximately twelve months after randomization, patients will return to the Clinical Research Center for the post-treatment visit, during which all factors measured at pre-treatment will be reassessed. Finally, research assistant will contact patients annually after their post-treatment visit to complete the follow-up calls, with the last call coming within 2 weeks of the study end date. These calls will follow the same procedures as the mid-treatment call.

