Our exploratory outcome, modeled after the JUPITER trial,¹⁹⁵ is time to first major CVD event, defined as: CVD death (ICD-10 I20-I25 or I60-I69 the first-listed cause of death); nonfatal MI (CK-MB >3.0 ng/ml, troponin >0.3 µg/L, or ICD-9 410); nonfatal stroke (ICD-9 430-432, 433.01, 433.11, 433.21, 433.31, 433.91, 434.01, 434.11, 434.91); unstable angina requiring hospitalization (inpatient admission ICD-9 411.1); and revascularization – i.e., percutaneous coronary intervention (ICD-9 00.66, 36.03, 36.06, 36.07, 36.09; CPT 92980-92984, 92995, 92996) or coronary artery bypass graft (ICD-9 36.10-36.19; CPT 33510-33536). Because recruitment will occur during Years 01-02, the mean observation period will be 4 years (1-year intervention period plus 3-year follow-

up period), with a range of 3-5 years. The Regenstrief programmer who worked on our IMPACT study³⁵ will identify candidate CVD events by searching the INPC every 6 months (blind to assignment), with the last search performed on the end date. To capture the small number of events that may occur outside of the INPC catchment area, patients will complete a CVD questionnaire at mid- and post-treatment and during the follow-up calls. If a reported event is not in the INPC, we will request medical records from the patient to confirm the event. Our cardiologist ([name]), also blinded, will use standardized criteria to adjudicate all CVD events for this exploratory outcome. [name] has served on endpoint committees for past trials. When needed, [name] will consult with the cardiologist on the DSMB (also blinded). Given that we are coding “harder” events and that many events will be positive for multiple markers, it is unlikely that coded events will be misclassified. We may fail to detect (and thus initially misclassify) a few events through INPC, which is why we are obtaining patient reports and medical records.

Atherogenic Behavioral Factors

The BRFSS Tobacco Use Questionnaire, International Physical Activity Questionnaire, and the Morisky Questionnaire (MMAS-8) will assess tobacco use, physical activity, and adherence to cholesterol and blood pressure medications, respectively. Each scale possesses strong psychometric properties.¹⁹⁶⁻¹⁹⁸

Conventional CVD Risk Factors

SBP and DBP will be the mean of the last 2 of 3 readings.¹⁹⁹ Fasting cholesterol, glucose, insulin, and HbA1c will be quantified using standard methods. BMI will be computed from measured height and weight.

Miscellaneous Factors

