7.0 Study Withdrawal/Discontinuation

All participants will be considered enrolled at the end of the ResNet interview. The informed consent statement describes the possibility of and the procedures for withdrawing from the study. A participant may notify either the principal investigator or any member of the research team at any time via email, phone, or in-person that s/he wants to withdraw from the study for any reason. The schedule of participant reimbursement is as follows: \$100 for the pre-treatment visit, \$25 for the mid-treatment call, \$100 for the post-treatment visit, \$20 for each of the annual follow-up calls, and up to \$10 per visit to cover parking or transportation costs. If a participant withdraws before the pre-treatment assessment visit, no payment will be provided.

Other reasons for study withdrawal/discontinuation are (a) the participant's primary care provider or another provider seeing the participant (e.g., a psychiatrist outside of the study team) no longer believes that his/her patient is appropriate for this trial after a triggering of the Suicidal Ideation Protection Protocol or any other reason, (b) the participant develops acute or serious illness that precludes completion of the main study visits within the allowed timeframes, and (c) the participant, in the assessment of the eIMPACT psychiatrist, exhibits evidence of a psychotic disorder or bipolar disorder (both of which are exclusionary conditions and could interfere with treatment delivery/effectiveness) during the 1-year treatment phase of the trial. In the case of situation (b), the patient will not complete any future study visits or calls. However, if the patient provides permission, electronic medical record data (e.g., incident CVD events) will still be obtained going forward, consistent with our Authorization Form. In the case of situation (c), patients with a psychotic disorder or bipolar disorder would likely benefit from psychotropic medications, such as antipsychotic medications or mood stabilizer, that are beyond what are provided in this trial.

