8.0 Statistical Considerations

Sample Size and Power Considerations

Endothelial Dysfunction

Using the effect size of depression treatment on FMD from our pilot trial, we need 88 patients (44 per arm) to detect a group difference in FMD of 1.7% ($d = 0.61$) at 12 months, assuming a power level of 0.80 and a Type I error of 0.05. This would be a clinically relevant difference. Assuming a conservative attrition rate of 20%,²⁰⁴ we will have 172 completers ($220 \times .80$) for FMD, yielding power levels of 0.98 for $d = 0.61$ and 0.80 for $d = 0.43$.

Candidate Mechanisms

We expect at a power level ≥ 0.80 for the candidate mechanisms (Hypotheses 2-5), as we will be able to detect effect sizes as small as $d = 0.43$ with 172 completers. In our IMPACT study³⁵ and pilot trial, effect sizes for depressive symptoms ($d = 0.69$ and 1.33), IL-6 ($d = 0.43$), and CRP ($d = 0.78$) were in the medium-to-large range. In other studies, effect sizes of 0.52 were found for psychological interventions on heart rate variability,²⁰⁵⁻²⁰⁷ 1.00 for SSRIs on IL-6,¹⁴³ 0.74 for SSRIs¹⁴³ and 0.85 for CBT¹³⁸ on CRP, 0.91¹⁴⁶ and 0.46¹⁴⁴ for SSRIs on BTG, and 0.87 for SSRIs on PF4.¹⁴⁴

CVD Events

Over the mean observation period of 4 years, we anticipate a cumulative CVD event rate of 20% (39 events) and a 25% lower relative risk ($HR \leq 0.75$) in eIMPACT versus usual care. These estimates are reasonable, as we observed a CVD event rate of 24% and a 46% lower relative risk (event rate: 18% vs. 31%) in our IMPACT secondary analysis that had a 4-year observation period. Our high-risk sample will differ from the typical sample of a risk reduction trial in that (a) all patients will have depression and ≥ 1 CVD risk factor and (b) many will be of low SES and/or African American, two groups at elevated risk for CVD event.^{1,171} Although we expect to have CVD event data for nearly all patients, we assume a conservative attrition rate of 10%, leaving 194 completers. As is typical of Phase 2 trials, our trial is not designed to detect a statistically significant difference in clinical events; however, a 25% relative risk reduction would be a clinically relevant signal (statin therapy reduces risk by $\approx 30\%$ ¹⁵⁶) and has been used to power recent event-driven Phase 3 cardiology trials.¹⁵⁷

Statistical Analyses

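### Section 7.0(b) ends telephone calls as well as clinic visits for patients too ill to attend, so SCL-20 and CVD self-reports that could still be collected are lost for illness-related reasons

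*Combined protocol and SAP*

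**What the plan says.** Section 7.0 lists situation (b) as a reason for discontinuation: "the participant develops acute or serious illness that precludes completion of the main study visits within the allowed timeframes". The stated result is that "the patient will not complete any future study visits or calls". What continues is record data only, and only by consent: "if the patient provides permission, electronic medical record data (e.g., incident CVD events) will still be obtained going forward".

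Section 5.0 (Overview, Visits, and Setting) describes the 6-month contact as a telephone call that opens with a CVD event questionnaire, after which "the self-reported scales completed at pre-treatment will then be readministered". The annual calls follow the same procedures. At 12 months, by contrast, "patients will return to the Clinical Research Center for the post-treatment visit", and no telephone alternative is described. The assessment table in 5.0 schedules depressive symptoms and CVD events at the calls as well as at the 12-month visit.

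Section 5.0 (CVD Events) gives the purpose of the questionnaire: "To capture the small number of events that may occur outside of the INPC catchment area, patients will complete a CVD questionnaire". Medical records are then requested when a reported event is not in the INPC.

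Section 8.0 promises an intent-to-treat analysis, tests the 12-month SCL-20 with a two-sample t-test, gives no missing-data method, and censors the Cox model only at non-CVD death or the end date.

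**The concern.** Being unable to attend a three-hour clinic assessment does not imply being unable to answer a telephone. Only FMD, heart rate variability, blood and physical measurements need attendance. Rule (b) nevertheless stops every later contact.

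Two outcomes are affected. The 12-month SCL-20, which tests Hypothesis 2, takes on the missingness of the clinic visit although the instrument is already used by telephone. That missingness is related to illness, and the t-test simply omits these patients despite the intent-to-treat statement. For the exploratory CVD outcome, patient report is the only route the plan gives to events outside the INPC. Rule (b) closes that route for the rest of follow-up.

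**Working it through.** **1. What (b) removes.** The main study visits are not defined. The natural reading is the two Clinical Research Center visits, at 0 and 12 months. Randomization takes place at the end of the first, so after randomization (b) acts mainly up to the 12-month visit. Set against the assessment table, a patient discontinued under (b) loses:
- the 6-month call, if (b) occurs before it;
- the 12-month visit, and with it the SCL-20. This is lost because visits end, no fallback exists, and the ban on calls rules one out;
- the 2-4 annual calls.

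**2. The plan's own power figures.** Inputs from 8.0: two-sided 0.05, equal arms, 172 completers (86 per arm). The two-sample t-test has noncentrality d × √(86/2).
- d = 0.61: 0.61 × 6.557 = 4.00, power 0.978 (stated 0.98).
- d = 0.43: 0.43 × 6.557 = 2.82, power 0.801 (stated 0.80).

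Both reproduce. (220 × 0.80 is 176, not 172; the gap does not matter here.)

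**3. Power for Hypothesis 2.** Section 8.0 cites d = 0.69 and 1.33 for depressive symptoms. At the smaller value, 0.69 × 6.557 = 4.52, power 0.994 with 172 completers. With 198 it is 0.998. Power is not the issue.

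**4. Effect of recovering (b) patients (share assumed).** If 1-10% of 220 (2-22 patients) fall under (b) and all give the SCL-20 by telephone, completers rise from 172 to 174-194. Power at d = 0.43 rises from 0.80 to 0.81-0.85.

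**5. Effect of a general 12-month telephone fallback (recovery assumed).** Of 220, 44 are lost at 20% attrition. Recovering 25-50% of them adds 11-22, giving 187-198 completers and power at d = 0.43 of 0.833-0.853, against 0.810 at 176. This covers losses for any reason and is not the effect of rule (b) alone.

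**6. Possible SCL-20 bias (inputs assumed).** If (b) removes shares s₁ and s₂ of the two arms, and those patients score δ SD worse than the rest of their arm, the completer difference is off by (s₁ − s₂) × δ. With share differences of 3-10 percentage points and δ of 0.5-1.0, this is 0.03 × 0.5 = 0.015 to 0.10 × 1.0 = 0.10 SD. With equal shares it is zero.

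**7. Undetected CVD events (inputs assumed).** Number under (b) × event rate × fraction outside the INPC. Low: 220 × 0.01 × 0.20 × 0.05 = 0.02. High: 220 × 0.10 × 0.40 × 0.20 = 1.8. These are totals over follow-up, against 39 planned events (0.20 × 194 = 38.8).

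**8. How such an event is analysed.** The Cox model does not censor at discontinuation. A discontinued patient with an undetected event therefore contributes event-free time to the end date.

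**The case against.** The strongest stronger reading is that an MI or stroke triggers (b), the patient is never asked about it, and the event is lost. The documents do not support that. The team can invoke (b) only if it knows of the illness, so an MI or stroke that triggers it is normally already known, and 5.0 provides for requesting records when a reported event is not in the INPC. The outcome is time to first event, so later events in that patient add nothing. What remains is a patient discontinued for another illness whose first CVD event comes later and outside the INPC.

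A reader might also infer a steady yearly loss of events throughout follow-up. The documents give no basis for one: (b) is tied to the main visits, out-of-network events are described as few, and INPC searches, including state death data, continue with permission. The 10% attrition allowed for event data in 8.0 already leaves room for some loss, and the outcome is exploratory.

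Sparing seriously ill people a 45-minute call is a reasonable aim, and 12-month timing is only approximate, so short illnesses may be absorbed. Both points stand, but a right to decline meets the burden concern without a blanket ban. It is also true that the 6-month and annual calls do not feed the 12-month t-test. The SCL-20 loss comes from the missing fallback at 12 months together with the ban.

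**Conclusion.** The concern holds as a data-collection flaw of modest size. The consequence of 7.0(b) is wider than its trigger, and following it discards obtainable data in patients who are missing because they are ill. The case rests on avoidable, illness-related missingness, not on power or on a count of lost events.

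The size cannot be fixed from the documents: they give neither the number of (b) patients, nor the split by arm, nor the share of events outside the INPC. The bias and event ranges above rest on assumed inputs, and the direction of any bias is unknown. The wording of the rule, the telephone use of the scales, the lack of a 12-month fallback and the censoring rule are all plain in the text.

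**What to change.** In 7.0(b), separate ending clinic visits from ending telephone follow-up. Clinic measures that cannot be done are skipped. The 12-month self-report scales, CVD questionnaire, depression-care interview and adverse-event questions are offered by telephone. Annual calls continue unless the patient declines.

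In 5.0, add the same 12-month telephone fallback for any patient who does not attend the Clinical Research Center, and record the mode of administration so that it can be examined in a sensitivity analysis.

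In 8.0, say how patients who decline calls or refuse record access are censored, and how a missing 12-month SCL-20 is handled.

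The cost is protocol wording and a few 45-minute calls with the existing script and staff. The downsides are some call burden for ill patients, who may decline, and a few 12-month scales given by telephone rather than completed online. No treatment rule changes.

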8.0 Statistical Considerations

Sample Size and Power Considerations

Endothelial Dysfunction

Using the effect size of depression treatment on FMD from our pilot trial, we need 88 patients (44 per arm) to detect a group difference in FMD of 1.7% ($d = 0.61$) at 12 months, assuming a power level of 0.80 and a Type I error of 0.05. This would be a clinically relevant difference. Assuming a conservative attrition rate of 20%,²⁰⁴ we will have 172 completers ($220 \times .80$) for FMD, yielding power levels of 0.98 for $d = 0.61$ and 0.80 for $d = 0.43$.

Candidate Mechanisms

We expect at a power level ≥ 0.80 for the candidate mechanisms (Hypotheses 2-5), as we will be able to detect effect sizes as small as $d = 0.43$ with 172 completers. In our IMPACT study³⁵ and pilot trial, effect sizes for depressive symptoms ($d = 0.69$ and 1.33), IL-6 ($d = 0.43$), and CRP ($d = 0.78$) were in the medium-to-large range. In other studies, effect sizes of 0.52 were found for psychological interventions on heart rate variability,²⁰⁵⁻²⁰⁷ 1.00 for SSRIs on IL-6,¹⁴³ 0.74 for SSRIs¹⁴³ and 0.85 for CBT¹³⁸ on CRP, 0.91¹⁴⁶ and 0.46¹⁴⁴ for SSRIs on BTG, and 0.87 for SSRIs on PF4.¹⁴⁴

CVD Events

Over the mean observation period of 4 years, we anticipate a cumulative CVD event rate of 20% (39 events) and a 25% lower relative risk ($HR \leq 0.75$) in eIMPACT versus usual care. These estimates are reasonable, as we observed a CVD event rate of 24% and a 46% lower relative risk (event rate: 18% vs. 31%) in our IMPACT secondary analysis that had a 4-year observation period. Our high-risk sample will differ from the typical sample of a risk reduction trial in that (a) all patients will have depression and ≥ 1 CVD risk factor and (b) many will be of low SES and/or African American, two groups at elevated risk for CVD event.^{1,171} Although we expect to have CVD event data for nearly all patients, we assume a conservative attrition rate of 10%, leaving 194 completers. As is typical of Phase 2 trials, our trial is not designed to detect a statistically significant difference in clinical events; however, a 25% relative risk reduction would be a clinically relevant signal (statin therapy reduces risk by $\approx 30\%$ ¹⁵⁶) and has been used to power recent event-driven Phase 3 cardiology trials.¹⁵⁷

Statistical Analyses

We will use the intent-to-treat approach.²⁰⁸ All tests will be two-tailed with $p < .05$ considered significant. Supplemental analyses of completers will be performed. We will assess for differences in all baseline factors. Due to randomization, we do not expect baseline group differences. Even so, any differences will be taken into account when interpreting results, and any baseline factors that differ between the groups will be included as covariates in sensitivity analyses. Aim 1: We will test our hypothesis that eIMPACT patients will exhibit greater improvement in endothelial dysfunction (Hypothesis 1) by performing a two-sample t-test with FMD at 12 months as the dependent variable. If there is a group difference in baseline FMD, analyses of covariance (ANCOVAs) adjusting for baseline level will also be performed. We will also explore whether eIMPACT patients show a clinically relevant reduction (25% lower relative risk) in CVD events by running a Cox proportional hazards model with treatment group predicting time to first CVD event. Patients will be censored at non-CVD death or the end date. We expect to observe a $HR \leq 0.75$. Aim 2: We will test our hypotheses that eIMPACT patients will exhibit greater decreases in the candidate mechanisms (Hypotheses 2-5) by performing two-sample t-tests with SCL-20 score, high-frequency heart rate variability, IL-6, CRP, BTG, and PF4 at 12 months as the dependent variables. If baseline group differences are found, ANCOVAs adjusting for baseline level will

also be performed. To explore whether decreases in the candidate mechanisms are associated with improvements in endothelial dysfunction, we will compute correlations between 12-month change in each mechanism and in FMD. To explore whether decreases in the candidate mechanisms are partial mediators of eIMPACT's hypothesized cardioprotective effect, we will conduct exploratory mediation analyses using MacKinnon's approach, which has greater power than others.²⁰⁹ First, to quantify the treatment effect on each mechanism ("a" coefficients), we will perform linear regressions with treatment group predicting 12-month level of each mechanism. Second, to quantify the effect of each candidate mechanism on endothelial dysfunction ("b" coefficients), we will perform linear regressions with 12-month level of each mechanism predicting 12-month FMD in the presence of treatment group. Third, the significance of each mediation effect will be tested using MacKinnon and Lockwood's product of coefficients ("ab") method employing asymmetric confidence limits.^{209,210} If this test is significant, the selected mechanism is a partial mediator of the treatment effect on 12-month FMD. Of note, we will also explore (a) if changes in depressive symptoms are correlated with changes in the atherogenic physiologic factors and (b) if changes in FMD predict CVD events.

Supplemental, Hypothesis-Generating Analyses

(1) We will explore atherogenic behavioral factors, conventional CVD risk factors, and depression care variables as potential mechanisms of eIMPACT's effect on FMD by repeating Aim 2 analyses. (2) To explore the separate effects of intervention components (which likely have shared and unique pathways; Figure 1), Aim 1 and 2 analyses will be repeated after coding the treatment variable as follows: eIMPACT both components, eIMPACT antidepressants only, eIMPACT psychotherapy only, eIMPACT neither component, and usual care. (3) We will explore sex and race/ethnicity as moderators of the treatment effect on the outcomes. (4) We will estimate the cost per patient of providing eIMPACT, including charges for BtB, DCS, psychiatrist and primary care expert supervision, materials, and a telephone line.

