We will leverage this unique resource to identify CVD events. The Indiana Network for Patient Care (INPC),^{117,118} the nation's largest clinical data repository (see Facilities and Other Resources), was an NIH-funded expansion of the Regenstrief Medical Record System,¹¹⁹ which has been used extensively for clinical research. The INPC contains 4.7 billion bits of standardized clinical data for 14.7 million patients from 19,000 physicians, 90 hospitals, and 110 clinics and other sites. The participating systems deliver registration records; coded diagnoses and procedures; laboratory, pathology, and vital signs data; emergency department, inpatient, and outpatient encounter data; and pharmacy data. INPC also gathers data from Indiana Medicaid and other commercial payers, as well as death data from the Indiana State Department of Health.

Advantages of our approach include minimal attrition and an observation period that can be easily extended. As in our IMPACT follow-up study,³⁵ we anticipate having event data for nearly all randomized patients, given that (a) we will identify most CVD events through INPC searches (no patient participation required) and (b) we have developed procedures (e.g., follow-up calls) to identify the few events that may occur outside of the INPC

catchment area. Extending the observation period to capture more CVD events would also require few resources, as it would involve the data manager re-running INPC search programs.

Proposed Research and Conceptual Framework

We will conduct a Phase 2 randomized controlled trial of 220 primary care patients aged 50+ years with a depressive disorder and CVD risk factors but no clinical CVD. Patients will be randomized to 12 months of eIMPACT or usual care and will be followed for a mean of 4 years. The conceptual framework guiding our trial is shown in Figure 1. Our central hypothesis is that eIMPACT will improve endothelial dysfunction by decreasing depressive symptoms, autonomic dysfunction, systemic inflammation, and platelet activation.

[figure not shown]

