Our long-term goal is to develop, optimize, and disseminate treatments to improve CVD outcomes of a large cohort of patients at elevated risk of CVD onset, poor CVD prognosis, and high healthcare costs. This project's objective is to test whether our modernized IMPACT intervention (eIMPACT), delivered before CVD onset, reduces CVD risk. We propose a Phase 2 randomized controlled trial of 220 primary care patients (≥ 50 years, 40% African American) with a depressive disorder and CVD risk factors but no clinical CVD. Patients will be randomized to 12 months of eIMPACT (a collaborative stepped care program including antidepressants and computerized and telephonic cognitive-behavioral therapy) or usual care (usual primary care for depression). Patients will be followed for a mean of 4 years. The primary outcome is endothelial dysfunction assessed by brachial flow-mediated dilation (FMD),⁸¹ which is considered a barometer of CVD risk.⁸⁸ Critically, intervention-related improvements in FMD predict a reduced incidence of CVD events.¹¹³⁻¹¹⁵ Our central hypothesis is that eIMPACT will improve endothelial dysfunction in depressed patients by decreasing depressive symptoms, autonomic dysfunction, systemic inflammation, and platelet activation, which are leading candidate mechanisms. We will test our central hypothesis by carrying out these specific aims:

Aim 1: Determine whether eIMPACT reduces the excess CVD risk of depressed patients. Depressed patients randomized to eIMPACT, versus usual care, will exhibit a clinically and statistically significant improvement in the primary outcome of endothelial dysfunction at the 12-month post-treatment visit (Hypothesis 1). We will also explore whether eIMPACT patients, versus usual care patients, show a clinically relevant reduction (25% lower relative risk^{156,157}) in CVD events (exploratory outcome) over a mean observation period of 4 years (1-year intervention period plus 3-year follow-up period).

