5.0 Study Procedures

Overview, Visits, and Setting

We will conduct a Phase 2 randomized controlled trial of 220 primary care patients aged 50+ years with a depressive disorder and CVD risk factors but no clinical CVD. Patients will be randomized to 12 months of eIMPACT, our modernized IMPACT intervention, or usual care and will be followed for a mean of 4 years.

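### The completer counts in the power section (172 and 194) do not follow from N = 220 and the stated attrition rates, which give 176 and 198

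*Combined protocol and SAP*

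**What the plan says.** The planned sample size is 220 wherever it is stated. Section 1.0 (Proposed Research and Conceptual Framework) describes a "randomized controlled trial of 220 primary care patients aged 50+ years"; Section 2.0 has "We propose a Phase 2 randomized controlled trial of 220 primary care patients"; Section 5.0 (Overview) has "We will conduct a Phase 2 randomized controlled trial of 220 primary care patients".

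Section 8.0 (Sample Size and Power Considerations) then makes three statements about completers:

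- Endothelial Dysfunction: attrition of 20%, so "we will have 172 completers", with the multiplication 220 × .80 printed beside the figure. Power is given as 0.98 at d = 0.61 and 0.80 at d = 0.43.
- Candidate Mechanisms: the trial can detect "effect sizes as small as $d = 0.43$ with 172 completers", which is offered as the basis for power of at least 0.80 on Hypotheses 2-5.
- CVD Events: "we assume a conservative attrition rate of 10%, leaving 194 completers". The paragraph anticipates a 20% cumulative event rate, given as 39 events.

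**The concern.** The document prints both factors of the first product and the wrong result. The second count misses by the same 4 patients, so this is not a single mistyped digit. Measured against 220, the printed counts imply higher attrition than the rates stated beside them.

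The count of 172 supports the stated power for the primary hypothesis and for Hypotheses 2-5. If it cannot be derived from the stated N and attrition, a reader cannot tell whether the power section describes the 220-patient trial set out elsewhere or one of another size. At stake is the traceability of the sample-size justification; the adequacy of the sample is not in doubt.

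**Working it through.** **Inputs.** N = 220 (Sections 1.0, 2.0, 5.0 and the product printed in 8.0); attrition 20% for FMD and 10% for CVD events (8.0); effect sizes d = 0.61 and d = 0.43 (8.0); Type I error 0.05 (8.0, sample size), two-tailed (8.0, Statistical Analyses); equal arms (8.0 gives 44 per arm for a total of 88).

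**1. Completer counts.** Completers = N × (1 − attrition).

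| Quantity | Calculation | Result | Printed | Gap |
|---|---|---|---|---|
| FMD completers | 220 × 0.80 | 176 | 172 | 4 (4/176 = 2.3%) |
| Event-data completers | 220 × 0.90 | 198 | 194 | 4 (4/198 = 2.0%) |

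Dividing by 1 plus the rate does not recover the printed counts either: 220/1.2 = 183 and 220/1.1 = 200.

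**2. Attrition implied by the printed counts.** 1 − 172/220 = 21.8% and 1 − 194/220 = 11.8%, against the stated 20% and 10%.

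**3. Are the printed powers consistent with 172?** Two-sample t-test, two-sided 0.05, n per arm, noncentrality d × √(n/2):

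| Completers | Per arm | Power, d = 0.61 | Power, d = 0.43 | d at 80% power |
|---|---|---|---|---|
| 172 (as printed) | 86 | 0.978 | 0.801 | 0.430 |
| 176 (from N = 220) | 88 | 0.980 | 0.810 | 0.425 |

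The printed 0.98 and 0.80 reproduce at 172. The required 44 per arm at d = 0.61 also reproduces: the t-test solution is 43.2, rounded up. So the power calculation is sound for 172 completers, and the fault lies in the step from 220 to 172.

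**4. Events.** 20% × 194 = 38.8, which matches the printed 39, so the rate appears to have been applied to completers. With 198 completers it gives 39.6, about 40. Applied to all 220 it would give 44.

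**5. What base would give the printed counts?** 172/0.80 = 215.0 and 194/0.90 = 215.6. A base of 216 (108 per arm) also fits if each arm is rounded down: 108 × 0.80 = 86.4, so 86 per arm and 172 in total; 108 × 0.90 = 97.2, so 97 per arm and 194 in total. The recruitment figures point the same way. In Section 4.0, 4,320 approached × 5% = 216. At 9 per month over the 24 months of Years 01-02 (Section 5.0, CVD Events), 9 × 24 = 216. This is inference, since no section states 215 or 216 as the sample size.

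**The case against.** The arithmetic itself cannot be contested. The best reply is that 172 and 194 may be the intended counts and 220 the figure that does not belong with them. The printed powers and the 39 events all agree with 172 and 194, and the recruitment projection yields 216, which explains both counts. On that reading the power section is internally sound and the remedy is to reconcile N, so replacing the completer counts should not be the only option.

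Part of this stands. The documents do not show which base the sponsor had in mind, so the sponsor should confirm it. But the recruitment figures are approximate projections and do not state a sample size. The power section itself names 220 as the multiplicand, and every stated N is 220. As written, the counts are wrong.

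The reply can also say that nothing turns on it. The error understates power, the pilot effect needs only 88 patients, about half of either count, and CVD events are exploratory with no claim to power. That is correct, and it is why the point is minor.

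**Conclusion.** The concern holds, as a minor point. Against N = 220, the FMD count should be 176 where 172 is printed, and the event-data count 198 where 194 is printed. Each is short by 4 patients, about 2%, in the conservative direction. Power at d = 0.61 is 0.98 either way; at d = 0.43 it is 0.81 where 0.80 is printed; the effect detectable with 80% power is d = 0.425, so the statement for Hypotheses 2-5 remains true. The anticipated event count moves from 39 to about 40.

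The power figures assume equal arms and a two-sided t-test at 0.05, as the plan specifies. The event figure assumes that the 20% rate applies to completers, which the printed 39 suggests but the text does not say. No hypothesis, analysis or recruitment target is affected.

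**What to change.** If 220 is the intended sample size, correct Section 8.0 as follows:

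- replace 172 with 176 (88 per arm) under Endothelial Dysfunction and under Candidate Mechanisms;
- restate power as 0.98 for d = 0.61 and 0.81 for d = 0.43, noting that d = 0.43 remains detectable with at least 0.80 power;
- replace 194 with 198 under CVD Events, state the base for the 20% event rate, and, if that base is completers, change 39 events to about 40.

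The recruitment estimate in Section 4.0 can stay in this case, because it is given as approximate.

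If a different N was used for the power section, state it and make Sections 1.0, 2.0, 5.0 and 8.0 agree with it. The sponsor should confirm which case applies.

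Under the first option the cost is a few figures in one section, with no change to design, analysis, recruitment or conduct.
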